6.1. Eligibility criteria

To be included in the investigation, the subjects must comply with the criteria presented below.

6.1.1. Inclusion criteria

Table 1: Inclusion criteria

Incl	usion criteria To be included in the evaluation a subject must comply with the following inclusion criteria:	Justification for inclusion criteria
1.	Has given written consent to participate by signing the Informed Consent Signature Form	To meet the Helsinki declaration
2.	Is at least 18 years of age and have full legal capacity	To meet the Helsinki declaration
3.	Has an ileostomy or colostomy with consistent liq- uid/mushy fecal output (5-7 Bristol scale*) *See appendix 2	The product is indicated for use with ileostomies and colostomies with liquid fecal output
4.	Is able to use one of the five test products (i.e. Ø40, Ø50, Ø60, Ø70, Ø80 mm)	The technical design of the device requires use of one of the five sizes
5.	Has experienced leakage** under the baseplate at least three times within the last fourteen days. **Leakage defined as output seeping under the baseplate" See Appendix 5, Figure 2-5	To ensure that the subjects have potential leakage which the sensor layer can react upon
6.	Has worry about leakage to "some degree, high degree, or very high degree" (on a five-point Likert scale: Very low degree/Not at all, Low degree, some degree, High degree, very high degree)	To ensure only subjects that worry about leakage are included
7.	Is willing to refrain from use of ostomy paste	The use of ostomy paste may influence system performance
8.	Has a smartphone compatible for Heylo™ application	To answer the CRF questions and handle the Heylo™ appli- cations, the subjects must have smartphones
9.	Is able to follow study procedures for 4 months (assessed by investigator or delegate)	To ensure low dropout rate

6.1.2. Exclusion criteria

Table 2: Exclusion criteria

	A subject is not allowed to participate in case he/she:	Justification for exclusion criteria:
1.	Is participating in other clinical investigations or has previously participated in this investigation	Other investigational guidelines/products may interfere with the investigational endpoints
2.	Is pregnant or breastfeeding	Even though the ingredients and the recipes have been approved for human beings, their effect on embryos, foetuses and infants are unknown
3.	Has known hypersensitivity towards any of the products used in the investigation	It is not ethical to include persons that know they are allergic to the products used in the investigation and it would also

Excl	usion criteria A subject is not allowed to participate in case he/she:	Justification for exclusion criteria:
		create bias, as these persons would give the product, they are allergic to a more negative rating and most likely also create an AE.
4.	Is using/ has a pacemaker	To protect the subjects from unnecessary harm, subjects with pacemakers are excluded

6.1.3. Pregnancy and breastfeeding

As specified in exclusion criteria number 2. pregnancy and breastfeeding are not allowed in this clinical investigation. All female subjects with childbearing potential (they have had at least one period during the last 12 months), must at V0 confirm that they are not pregnant or breastfeeding. They will also be informed that no pregnancy is allowed during the investigation.

If the subject becomes pregnant during the Clinical investigation, it is important, that the subject informs the Principal investigator or delegate immediately. The PI will then consider whether she should continue in the investigation.

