6.3. Subject withdrawal criteria

The subject is allowed to withdraw from the investigation at any time for whatever reason without any consequences for their future treatment outside the clinical investigation. The Investigator may withdraw a subject from the investigation at any time if they judge it to be the subject's interest.

The investigator must withdraw a subject from the investigation due to:

- Major noncompliance with the CIP impacting the scientific integrity of the investigation.
- If subject's safety and wellbeing is compromised by further participation.
- Subjects lost to follow-up. At least three documented attempts will be made to verify subjects lost to follow-up.

Withdrawn subjects will not be replaced by new subjects.

A subject who is withdrawn from the investigation, for any reason, will be encouraged to contact the investigator if problems arise that the subject believes are related to the clinical investigation. Subjects who have not experienced any adverse events will not be followed up. For subjects who experience adverse events, see section 18.5.

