18.4. Serious adverse events (SAE)

A serious adverse event is an adverse event that:

- Led to death.
- Led to a serious deterioration in the health of the subject, users or other persons as defined by one or more of the following:
 - 1) a life-threatening illness or injury, or
 - 2) a permanent impairment of a body structure or a body function including chronic diseases, or
 - 3) in-patient or prolonged hospitalization, or
 - 4) medical or surgical intervention to prevent life-threatening illness or injury or permanent impairment to a body structure or a body function.
- Led to foetal distress, foetal death, a congenital abnormality, or birth defect including physical or mental impairment.

This includes device deficiencies that might have led to a serious adverse event if:

- 1) Suitable action had not been taken, or
- 2) Intervention had not been made, or
- 3) Circumstances had been less fortunate.

These are handled under the serious adverse event reporting.

Planned hospitalization for a pre-existing condition, or a procedure required by the CIP, without serious deterioration in health, is not considered a serious adverse event.

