18.5. Medical care of subjects

Principal investigator shall ensure that adequate medical care is provided, during and after participation in the clinical investigation, to a subject experiencing an adverse event. All ongoing ADEs, SAEs, SADEs and DDs that could have led to a SAE at subject termination will be followed according to the Risk Benefit analysis (see 8.2) and will be followed until a resolution is addressed for a period of 2 months after subject termination. An ongoing adverse event at subject termination visit is documented as the current status for the adverse event and will not be followed up.

The subjects shall be informed of any new significant findings occurring during the clinical investigation, including the need for additional medical care that can be required, and of the nature and possible cause of any adverse events experienced.

Principal investigator or delegate shall provide the subject with the necessary instructions on proper use, handling,

storage and return of the investigational device when it is used or operated by the subject.

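### Sections 6.3 and 18.5 do not secure the foetal and birth outcomes that 18.4 counts as serious once a pregnant subject has been withdrawn or has passed V3

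*Combined protocol and SAP*

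**What the plan says.** **Entry and conduct.** Section 6.1.3 refers to exclusion criterion 2 and states that "pregnancy and breastfeeding are not allowed in this clinical investigation". Women of childbearing potential "must at V0 confirm that they are not pregnant or breastfeeding", and "They will also be informed that no pregnancy is allowed during the investigation". If a pregnancy occurs anyway, the subject is to tell the PI or delegate at once, and "The PI will then consider whether she should continue in the investigation". No criteria for that decision are given.

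**Reason for the exclusion.** Table 2 in section 6.1.2 explains that although the materials are approved for human use, "their effect on embryos, foetuses and infants are unknown".

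**Withdrawal.** Section 6.3 lists three grounds on which the investigator must withdraw a subject, and pregnancy is not among them. It also lets the investigator withdraw a subject at any time in her own interest. On what follows a withdrawal it says "Subjects who have not experienced any adverse events will not be followed up", and it refers subjects with adverse events to section 18.5. Any withdrawn subject is encouraged to get in touch about problems she believes are related to the investigation.

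**Safety follow-up.** Section 18.5 follows ADEs, SAEs, SADEs and device deficiencies with SAE potential that are ongoing at termination, "for a period of 2 months after subject termination". An ordinary adverse event still ongoing at termination is recorded as it stands and not followed.

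**What counts as serious.** Section 18.4 includes an event that "Led to foetal distress, foetal death, a congenital abnormality, or birth defect". Section 18.7 has the PI assess events during the investigation and requires SAEs to reach the sponsor within 24 hours of awareness.

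**The concern.** The plan names an unknown risk to the foetus and infant and classes its consequences as serious. It then sets follow-up rules that stop well before most of those consequences would be seen. A subject withdrawn only because she is pregnant has, on a plain reading of the definition in 18.1, had no adverse event, so 6.3 ends contact with her. A subject who completes V3 with an uneventful pregnancy has nothing ongoing that 18.5 would follow.

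What is at stake is how a blank in the safety tables would be read. If a pregnancy occurs and the report shows no foetal or birth event, the reader cannot tell a normal outcome from one nobody asked about. The trial's efficacy answer is not touched.

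**Working it through.** The plan gives no figure to reproduce here. The check sets its follow-up rules against a pregnancy timeline.

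**Inputs from the plan**
- Time on study: 16 weeks, ±6 days (section 5.1).
- Longest safety follow-up: 2 months after termination (section 18.5), taken as 2 × 30.4 / 7 = 8.7 weeks.

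**Assumption not in the plan**
- Term is 38 weeks after conception (40 weeks' gestation). The range considered is 35 to 38 weeks after conception (37 to 40 weeks' gestation).

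**Step 1: latest planned contact.** 16 + 8.7 = 24.7, or about week 25. This applies only to a subject who has a qualifying event ongoing at termination. For anyone else who completes, the last planned contact is V3 at week 16.

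**Step 2: gap to term.** For conception at study week *c*, term falls at week *c* + 38.

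| Conception at week | Term at week | Gap after V3 (week 16) | Gap after V3 + 2 months (week 24.7) |
|---|---|---|---|
| 0 | 38 | 22 | 13.3 |
| 8 | 46 | 30 | 21.3 |
| 16 | 54 | 38 | 29.3 |

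The smallest gap for an on-study conception is therefore about 13 weeks.

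**Step 3: withdrawal without an adverse event.** As an illustration, take conception at V1 and withdrawal at week 6. Section 6.3 provides no further contact, so the gap to term is 38 − 6 = 32 weeks.

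**Step 4: sensitivity.** Using the full +6 days, the latest contact is 16 + 0.9 + 8.7, or about week 25.5, and the smallest gap is 38 − 25.5 = 12.5 weeks. Placing term at 35 weeks after conception gives 35 − 24.7 = 10.3 weeks, or 35 − 25.5 = 9.5 weeks with the window added. A term birth from an on-study conception falls outside every planned contact in all of these cases.

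**Step 5: what the rules would catch.** In a subject who continues, Table 4 schedules assessment of adverse events at V1, V2, V3 and both follow-up calls, and 18.7 requires rapid SAE reporting. With conception at V1, gestational age is 16 + 2 = 18 weeks at V3. A foetal loss, or an abnormality found before birth, could occur by then and would be reported. Table 4 has no pregnancy item, and the only pregnancy check in the text is the confirmation at V0.

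**Step 6: pregnancies that began before V0.** If an unrecognised pregnancy began 4 to 12 weeks before V0 (an assumed range), gestational age at V3 + 2 months is about 31 to 39 weeks. Birth could then fall inside the longest window, but only for a subject already being followed for a qualifying event.

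**The case against.** The strongest reply is that the plan is neither silent nor contradictory. An investigator may withdraw any subject in her own interest, adverse events are asked about at every visit from V1 and at both calls, SAEs go to the sponsor within 24 hours of awareness, and withdrawn subjects are encouraged to make contact. The device is a CE-marked external sensor layer whose risks section 8.2 equates with those of marketed ostomy products. No foetal safety claim is planned, and few pregnancies are to be expected.

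Much of this stands, and it rules out three stronger readings that a reader might infer.

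- *That no foetal or birth outcome could ever be recorded.* The documents do not support this. Foetal distress or death can occur within the 16 weeks in a subject who continues, and sections 7.2 and 18.7 would capture it. The gap concerns outcomes after withdrawal or V3.
- *That 6.1.3 contradicts itself.* It reads more naturally as a prohibition followed by a provision for the case where pregnancy happens anyway, and the PI's decision fits the general withdrawal power in 6.3. What remains is loose wording: subjects are told pregnancy is not allowed during the study, no criteria guide the PI, and 6.3 does not mention pregnancy.
- *That individual study nurses could apply opposite rules.* Section 6.1.3 gives the decision to the PI. A delegate may receive the news but is not given the decision.

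The reply does not close the gap itself. Self-contact is passive and limited to problems the subject already believes are related. The reporting duty in 18.7 depends on someone becoming aware. Treating pregnancy itself as an ordinary adverse event would not help either, because 18.5 does not follow those beyond termination.

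**Conclusion.** The point holds as a gap in safety data collection. Under 6.3 and 18.5 as written, nothing ensures that the foetal and birth outcomes listed in 18.4 are collected after a pregnant subject is withdrawn or passes V3. For a pregnancy conceived on study, a term birth falls at least about 13 weeks after the latest planned contact, assuming term at 38 weeks after conception and the nominal schedule. With an earlier term and the full visit window, the figure is 9.5 weeks. Such outcomes may go unrecorded; it cannot be said that they will.

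The size of the problem depends on how many pregnancies occur. The documents give no expected number, and it is likely to be very small. This is an inexpensive improvement, with no bearing on the primary analysis, sample size or multiplicity. The wording of 6.1.3 alongside 6.3 is a lesser, separate matter of reconciliation.

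**What to change.** Add to sections 6.3 and 18.5 that a subject who becomes pregnant after enrolment is contacted, with her agreement, until the outcome of the pregnancy is known. This should apply whether she continues or is withdrawn, and whether or not she has had an adverse event. State that the outcome is recorded and, where it meets 18.4, reported under 18.7.

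Separately, reconcile the wording of 6.1.3 (pregnancy not allowed, the PI considers continuation) with the withdrawal provisions in 6.3. Which continuation or withdrawal rule applies is for the sponsor and investigator to settle, and none is proposed here.

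The cost is a few sentences of text and one or two telephone contacts for each of the very few subjects concerned.

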6.2. Recruitment and enrolment

Recruitment of potential subjects will begin once approval have been obtained from the Ethics Committee (EC). It is estimated that the recruitment process will be completed within 8 months.

Table 3: Table showing an overview of the recruitment process.

Recruitment method	Coloplast Database
Potential subjects	
First contact	
Second contact	If potential subjects return the Reply Letter/reply to the email or have called the investigator as first contact and are interested, the Principal Investigator or delegated will contact the subjects by phone and give a short introduction to the investigation and go over the inclusion and exclusion criteria. If the subjects do not meet the inclusion criteria or meet the exclusion criteria, this will be registered at the Subject Screening Log.
Subject Information Form	If subjects are eligible and interested in participating, then written information about the investigation (subject information) will be sent to the subjects to ensure that they are given the opportunity to read about the investigation before a possible informational visit, and for them to prepare any possible questions they may have. The subject information provides information to subjects about how to contact the Principal investigator or a delegated thereof, if they wish to learn more about the study.
First visit Information visit	If an eligible subject is interested in participating after the first contact, a visit will be arranged at subject's own home or remotely. When arranging the visit, it will be ensured that the subject has received the Information Form prior to the visit. The subjects will receive both written and verbal information about the possibility of bringing a companion to the informational visit and to any possible subsequent visits. See section 16 for information to be given to the subjects, as well as the informed consent process.
Enrolment and in- clusion visit (V0)	The subjects have the right to wait minimum 24 hours before deciding on participation. If/when the subject decides to participate, he/she will be asked to sign the relevant forms (see section 16).

If a subject so desires, and it is certain that it is understood what the investigation entails, and the relevant forms have been signed the subjects are considered enrolled in the investigation.

6.3. Subject withdrawal criteria

The subject is allowed to withdraw from the investigation at any time for whatever reason without any consequences for their future treatment outside the clinical investigation. The Investigator may withdraw a subject from the investigation at any time if they judge it to be the subject's interest.

The investigator must withdraw a subject from the investigation due to:

- Major noncompliance with the CIP impacting the scientific integrity of the investigation.
- If subject's safety and wellbeing is compromised by further participation.
- Subjects lost to follow-up. At least three documented attempts will be made to verify subjects lost to follow-up.

Withdrawn subjects will not be replaced by new subjects.

A subject who is withdrawn from the investigation, for any reason, will be encouraged to contact the investigator if problems arise that the subject believes are related to the clinical investigation. Subjects who have not experienced any adverse events will not be followed up. For subjects who experience adverse events, see section 18.5.

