V3 will also be the termination visit unless a situation occurs where a subject terminates earlier than expected. If this is the case the subject will as the last visit have the termination visit performed.

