- Schedule follow up call 7 days ±2 days after V1 to ensure compliance with the provided investigational device and study procedures and Insurance of subject's wellbeing.
- Schedule visit 2 in 8 weeks ±3 days

Visit 2 (V2), Week 8:

- Insurance of subject's wellbeing and follow-up on subject's compliance with study specific procedures (e.g. completing questionnaires and use of Investigational device + Standard of Care OR Standard of Care only)
- Subject completing todays questionnaires:
 - Emotional Impact (OLI)

- Coping and in control (OLI)
- Usual and Social activities (OLI)
- WHODAS 2.0:
 - Understanding and communicating
 - Getting around
 - Self-care
 - Getting along with people
 - Life activities
 - Participation in society
- Feeling of security, see section 5.3 and Appendix 4
- Assessment of:
 - o Leakage outside baseplate, see section 5.3 and Appendix 4
 - o Change in current stoma product, see section 5.3 and Appendix 4
 - o Change in Heylo size, if relevant, see section 5.3 and Appendix 4
 - o Review of AEs, ADEs, SAEs, SADEs, Device deficiencies and protocol deviations
- Instruct subject in installation of Heylo™ app (on subjects' own smartphone), if relevant
- According to the randomization, instruct subject in use of Heylo™ + Standard of Care or only Standard
 of Care for the next 8 weeks.
- Provide Investigation device Heylo™ after measurement of Heylo size, if relevant according to randomization.
- Instruct and remind the subject to follow the study specific procedures between visits, and inform subject to complete following questionnaires:
 - o Emotional Impact (OLI) every 2nd week
 - Coping and in control (OLI) every 2nd week
 - Usual and Social activities (OLI) every 2nd week
 - o Leakage outside baseplate 2nd week
 - WHODAS- every 4th week:
 - Understanding and communicating
 - Getting around
 - Self-care
 - Getting along with people
 - Life activities
 - Participation in society
- Collect unused Heylo™ devices from subjects who have tested these in the first 8 weeks.
- Collect used Heylo[™] devices (only charger and transmitter), from subjects who have tested these in the first 8 weeks
- Schedule follow up call 7 days ±2 days after V2 to ensure compliance with the provided investigational device and study procedures and Insurance of subject's wellbeing.
- Schedule visit 3 in 8 weeks ±3 days

Visit 3 – Termination Visit (V3), Week 16:

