- Insurance of subject's wellbeing and follow-up on subject's compliance with study specific procedures (e.g., completing questionnaires and use of Investigational device + Standard of Care OR Standard of Care only)
- Subject completing todays questionnaires:
 - Emotional Impact (OLI)
 - Coping and in control (OLI)
 - Usual and Social activities (OLI)
 - WHODAS 2.0:
 - Understanding and communicating
 - Getting around
 - Self-care
 - Getting along with people
 - Life activities
 - Participation in society
 - Feeling of security, see section 5.3 and Appendix 4

- Assessment of:
 - Leakage outside baseplate, see section 5.3 and Appendix 4
 - Change in current stoma product, see section 5.3 and Appendix 4
 - o Change in Heylo size, if relevant, see section 5.3 and Appendix 4
 - o Review of AEs, ADEs, SAEs, SADEs, Device deficiencies and protocol deviations
- Collect unused Heylo™ devices from subject who have tested this in the last 8 weeks
- Collect used Heylo[™] devices (only charger and transmitter), from subjects who have tested these in the last 8 weeks
- Termination and completion of the study

Follow-up call - Performed 7 days ±2 days after visit 1 and visit 2:

- Ensure compliance with the provided product and study procedures
- Insurance of subject's wellbeing.

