10.1.1. Definition of analysis populations

Intention to Treat (ITT) and Safety populations will be defined at a formal data review meeting before database lock. As a minimum, the data manager, the clinical manager, and the statistician will be involved in the classification of subjects.

The ITT population (full analysis set) will be constituted by all randomised subjects with valid informed consent who have been exposed to at least one product, with information on at least one endpoint.

The Safety population will constitute by subjects who have given informed consent.

All statistical analysis will be based upon the ITT population whereas adverse events and device deficiencies will be assessed based on the safety population. Invalid individual data points may be omitted from analysis even though the corresponding subject is part of the ITT population. Any exclusion of data points will be documented.

A formal per protocol (PP) population is not planned due to the explorative nature of the investigation. Considering the data obtained it might be considered to make additional explorative analyses based on a subset of the ITT population.

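### Mandatory withdrawal for undefined major noncompliance (section 6.3), with no outcome data planned after the termination visit, can remove scores that the ITT analysis needs

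*Combined protocol and SAP*

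**What the plan says.** Section 6.3 lists reasons for which the investigator must, not may, withdraw a subject from the investigation. The first is "Major noncompliance with the CIP impacting the scientific integrity of the investigation". The section does not define this. It adds "Withdrawn subjects will not be replaced by new subjects" and "Subjects who have not experienced any adverse events will not be followed up". Withdrawn subjects with adverse events are referred to section 18.5, which deals with safety follow-up and not with questionnaires.

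On compliance, the V2 procedures in section 7.1 follow up on "compliance with study specific procedures (e.g. completing questionnaires and use of Investigational device + Standard of Care OR Standard of Care only", and V3 repeats the item. The baseline visit includes "Schedule follow up call 7 days ±2 days after V1 to ensure compliance", and a matching call follows V2. Section 5.1 allows unscheduled contacts.

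On early stopping, section 5.1 says: "If this is the case the subject will as the last visit have the termination visit performed". The flow-chart in section 7.2 has one column for V3 and the termination visit. It contains the OLI domains, WHODAS and feeling of security. The V3 list in section 7.1 ends with "Termination and completion of the study".

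On analysis, section 10.1.1 says "All statistical analysis will be based upon the ITT population". Adverse events and device deficiencies use the safety population, and no per-protocol population is planned. Section 10.1.2 fits a mixed model to the scores at weeks 2, 4, 6 and 8 of each period and tests the week-8 difference.

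**The concern.** An ITT comparison needs outcomes from randomised subjects whether or not they used the device. If a subject is withdrawn because Heylo was not used, the remaining scheduled scores are never collected, and the reason they are missing is adherence. The mixed model then treats the gap as ignorable given the observed scores. If non-users benefit less and these withdrawals fall mainly in the Heylo period, the week-8 estimate moves from the effect in all randomised subjects toward the effect in compliers.

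Two features add to this. The trial is open-label and the sponsor's homecare nurses run the visits (section 6), so an undefined trigger would be applied with the treatment known. Blinding the statistician until database lock (section 5.8) cannot restore scores that were not collected. In addition, section 10.1.2 does not say how a termination score taken off schedule enters a model with four fixed time points.

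**Working it through.** **The plan's own figures.** Section 10.2 gives 108/0.75 = 144, which is exact. It states 81% power for a paired two-sided test at 0.025 with difference 6. The SD of the difference is 14.4 × √2 = 20.36, which gives 79.4% by the normal approximation and 78.4% by the exact paired t. The point here does not depend on that gap; only the variances and the difference of 6 are used below.

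**Inputs from section 10.2.** Residual variance 14.4² = 207.36. Between-subject variance 20.6² − 14.4² = 424.36 − 207.36 = 217. N = 144.

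**Assumptions, not in the documents.** Sequences of equal size, no other drop-out and no true period effect. Compliers gain 6 points at every week. A share q does not use Heylo, gains g, and is withdrawn for it during the Heylo period.

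**Method.** Expected estimate from the section 10.1.2 model (product, time, product × time, period, random subject) by generalised least squares: β = (Σ X′V⁻¹X)⁻¹ Σ X′V⁻¹E(y), with V = 207.36·I + 217·J (I the identity matrix, J a matrix of ones). The week-8 product contrast is read off. The target is the effect in all randomised subjects, 6(1 − q) + g·q.

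**Check on precision.** With everyone followed, SE = √(2 × 207.36/144) = √2.88 = 1.70. With 10% withdrawn it is 1.72 to 1.77.

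**Scores kept.**
- Acted on at V2 or V3: sequence A keeps its four Heylo scores and loses all four Standard of Care scores; sequence B loses nothing.
- Acted on earlier: later Heylo scores are lost too, and in sequence A the whole Standard of Care period.

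**Results with g = 0.**

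| When acted on, and use of the termination score | q = 10% | q = 20% |
|---|---|---|
| Everyone followed (target) | 5.40 | 4.80 |
| Day-7 call, termination score entered at week 8 | 5.55 | 5.09 |
| After week 2, termination score entered at week 8 | 5.60 | 5.19 |
| At V2/V3 | 5.64 | 5.28 |
| After week 2, termination score entered at week 4 | 5.91 | 5.82 |
| After week 2, termination score not used | 5.95 | 5.89 |
| Day-7 call, no Heylo score used | 6.00 | 6.00 |

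At 10% the bias runs from 5.55 − 5.40 = 0.15 to 6.00 − 5.40 = 0.60. Against the SE, 0.60/1.70 = 0.35. At 20% it runs from 5.09 − 4.80 = 0.29 to 6.00 − 4.80 = 1.20. That is an upper case, since it alone uses 20/25 = four-fifths of the planned drop-out. At 5% the target is 5.70, against 5.82 (V2/V3), 5.97 (after week 2, termination score not used) and 6.00 (day-7 call).

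**Effect of g.** The bias is proportional to 6 − g. With g = 3 it is halved: at 10% the target is 5.70, against 5.82, 5.97 and 6.00 for the same three timings. With g = 6 it is zero.

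**Effect of the termination score.** For withdrawal after week 2 at 10%, the estimate is 5.95, 5.91 or 5.60, depending only on whether and where that score is entered.

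**The case against.** The strongest objection is that the trigger is inferred. Section 6.3 requires noncompliance that is both major and harmful to scientific integrity. Device use appears in section 7.1 only as an example within a routine check, and the day-7 call is corrective in purpose. Section 13 classes a significant effect on data integrity as a major deviation and asks for reporting and a record of corrective action, without mentioning withdrawal. This stands: a reader might infer that the plan withdraws Heylo non-users, but no section says so. What remains is a mandatory rule with an undefined trigger, and sections 6.3 and 13 that do not say when such noncompliance ends participation.

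A reader might also infer that withdrawal leaves no outcome data. The documents do not support that, because the termination visit carries the OLI and WHODAS questionnaires. Entered at week 8, that score removes most of the bias in the early-withdrawal cases. Some bias remains under every entry examined, and the plan does not choose among them.

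The bias also needs several conditions together: non-use treated as major, concentration in the Heylo period, and less benefit in non-users. Compliance is checked in both periods, and acting at V3 in sequence B costs no scheduled score. All of this is fair and limits the size.

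Finally, section 10.1.1 lets invalid data points be omitted. A reader might take this to cover scores from noncompliant subjects, but the section draws no such link and requires exclusions to be documented.

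**Conclusion.** The concern holds as a conflict between a withdrawal rule and an analysis principle. Followed as written, section 6.3 can end outcome collection because of adherence, while the endpoint analyses are ITT. Bias is not automatic. On the assumed 10% non-use with no gain in non-users, it is about 0.15 to 0.60 points toward a larger effect, at most about a third of a standard error; with equal benefit it is zero. The non-use rate, the non-users' outcome and the timing are all assumptions.

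The documents do not support a conclusion that the primary analysis becomes per-protocol or that its result would be invalid. This is a cheap improvement that should be made, because scores not collected during the trial cannot be recovered afterwards.

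**What to change.** - **Section 6.3:** state that noncompliance, including not using the device, does not by itself end data collection. Subjects who have not withdrawn consent keep receiving the scheduled electronic questionnaires to week 16 and are analysed in their randomised sequence.
- **Sections 6.3 and 13:** reconcile them on what counts as major noncompliance and what follows from it.
- **Section 10.1.2:** prespecify whether and at which time point an early-termination score enters the model, because this choice changes the estimate. It will still matter for subjects who leave for other reasons.
- **Optional, section 10.1.1:** add that a score is not invalid merely because the subject was noncompliant.

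Decisions on stopping the device and safety withdrawals are unchanged.

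The cost is a few sentences in an amendment notified to the ethics committee (section 12). Subjects already answer through an electronic link (section 11.1.1), so the added work is mainly reminders, plus the V2 and V3 contacts if these are kept. The estimate may be smaller because non-users count. On the plan's paired-t basis with 10% non-use, no gain in non-users and no other drop-out, power is 82% with all 144 measured (difference 5.4), against 86% with 130 compliers (difference 6).
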